# Study Design:

It will be a prospective, randomized, single-blinded study. The study device will be used for only 2 days during the post-surgery hospital stay. The patients will be followed until their 6 weeks post-op office visit. We aim to finalize the study in 6 months.

Before enrollment into the study: During their pre-operative visit, patients will fill out a short questionnaire (The Pain Catastrophizing Scale, PCS short form) to assess their eligibility for the treatment and create a homogenized group of patients. Inclusion criteria is detailed below. 50 patients who are eligible for the study will be enrolled by written consent. Informed written consent will be obtained by PI ([name]) and the health care professional team ([name] and [name],PA ) during pre-operation office visit.

Once the patient volunteers to enroll to the study, we will establish their patient-specific intensity during their pre-op office visit. We will plan to have patient establish their correct and comfortable intensity before their surgery. The device comes in a carrying case with all the set supplies. At the time of placement, a health care provider will place the pre-packaged sterile electrode roughly 7-10 cm above and below the knee for testing or just above and below the

dressing during on the operated knee. Each set of electrodes will then be connected via a lead wire to the stimulation device.

Establishing the correct and comfortable intensity before operation will be as follows: The stimulation device which has a large power button will be turned on but provide no initial signal intensity. The patient will then be instructed to use the "plus" arrow on the device to slowly increase the signal intensity. The goal is to reach a point of intensity that feels strong but comfortable. The best method is to continue to increase to the point where it becomes slightly uncomfortable and the patient may experience some muscle fasciculations. Once that point is reached, decrease the intensity slightly and then use that intensity for their treatment. This patient specific intensity will be recorded and used for the IFC treatment.

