Enrolled patients will be randomly assigned to either **i. IFC treatment or ii. Placebo group** after their surgery. Patients in both groups will continue their regular standard post-operative care in addition to the IFC (or placebo) treatment. In addition to their post-operative standard of care, both groups will receive IFC treatment (or Placebo treatment) two times a day, for two days during their post-op hospital stay.

i. For the IFC treatment group: In addition to their post-operative standard of care, the IFC group will receive IFC treatment two times a day, for two days during their post-op hospital stay. The specific intensity of the IFC signal is patient specific. We will use previously established intensity values for each patient.

Once the intensity is set the program will lock automatically after 1 minute of inactivity or can be manually locked using the "star" button on the device. There is some degree of subjectivity in this portion but that is what provides the user with a patient specific signal. The signal intensity can go up to "100" on the device. The device works for 30 minutes at a time. On the device there is a timer which shows the time and it will automatically turn itself off after 30 minutes. During the time when the device is working, the patient can do any regular activity such as ambulating, physical therapy or sleep without concern.

The electrode has an adhesive pad that can remain on the patient post-operatively if desired or can be removed and replaced for each treatment session. The individual electrodes are re-usable and will be assigned to each patient.

For Placebo group: The standard of care and their physical therapy will not be altered for the placebo group. One set of the devices are programmed to be the placebo devices. The placebo devices can give a sensory stimulus so that the patient will feel the device is being on, but they will not have the therapeutic stimulus. We will monitor and record the same post-surgery outcomes as for the treatment group.

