The outcomes will be monitored in the immediate post-operative period by the Orthopaedic Surgery clinical team at Wakefield Hospital as well as at during the first post-op visit by [name] office by physician assistant ([name],PA) and nurse practitioner ([name]). The average hospital stay for TKA patients in the hospital (Wakefield) varies between 48-72 hours post-operatively. Typically, patients have a follow-up visit at 2 weeks and 6 weeks after surgery in the Hutchinson Campus, Tower 1 Orthopaedic Surgery Department clinic.

1. Primary outcome will be the post-operative pain medication usage during the first 24 and 48 hours. Daily opioid use will also be accounted based on electronic medical record reported by the patient's nurse after providing the patient with the specific medication. In addition, patients will be asked to rate their pain based on a set VAS pain scale twice a day before the IFC treatment.

2. Secondary outcomes Fitness for discharge on postoperative day 1and day 2 this will be measured utilizing the AM-PAC "6-Clicks" Basic Mobility Inpatient Short Form. The "6-Clicks" tool measures functional ability by having an assessor rate a patient's ability to perform physical tasks such as turning over in bed, moving from a bed to chair, and climbing steps. Scores are tallied to a total of 24 possible points, giving a quantitative measure of a patient's ability to perform these tasks. We will also use the `time` to reach the discharge as the outcome, pain scores recorded by nursing and physical therapy, complications, and any 30-day post discharge emergency department ED visits. Range of motion will be recorded during the daily physical therapy sessions by PT professionals with a goniometer. Range of motion then be assessed again in clinic at the first post-operative visit. Edema- thigh circumference will be calculated at the superior pole of the patella both prior to the surgery and daily post-operatively.All these outcome scores are done routinely as standard of care and they are recorded in patients charts in EPIC.

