# **Risk/Benefit**

#### Risks

i. Skin irritation: four prior studies mention skin irritation or thermal damage with IFC use [10-13]. Two of these studies were using IFC materials from older generation products [10, 11]. In one case report by Ford et al. [13] using IFC after total knee arthroplasty, the issues was theorized to be due to placement near the infrapatellar branch of the saphenous nerve which can be frequently insensate after total knee arthroplasty.

1. In order to limit risk, leads will be placed above and below the dressing to avoid skin irritation due to insensate skin.

2. Patient determined settings will be recorded during pre-operative visit prior to anesthesia local nerve block/spinal injection to prevent patients with slightly diminished sensation post-operatively from using too high a setting.

Loss of concentration, drowsiness, decreased alertness- One case report described a patient having temporary symptoms of loss of concentration, drowsiness, decreased alertness and gait disturbances for 4-5hours after IFC treatment. The reason was theorized to be opioid like reaction due to endogenous opioid release [14]. Although a rare risk, patients will be monitored in the hospital setting by medical staff throughout their admission and use of IFC treatment.

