# 4. Data analysis

We hypothesize that IFC therapy will improve patient's pain management and range of motion as well as decrease soft tissue edema after TKA when compared to control group. Study variables: total opioid consumption per 24h and 48h, VAS pain scale, KOOS pain score, range of motion, thigh circumference, 6-click AMP scores.

The significance level of the test was targeted at 0.05.

All outcomes and PT exam measures will be summarized as mean, standard deviation, and range. Differences between means will be analyzed with a Student's t-test or Mann-Whitney U test.

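### The study VAS is rated only before sessions, so it can show only carried-over relief, and the fourth session has no VAS follow-up

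*Combined protocol and SAP*

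**What the plan says.** On treatment, the Study Design says that "both groups will receive IFC treatment (or Placebo treatment) two times a day, for two days during their post-op hospital stay". On session length it says "The device works for 30 minutes at a time" and that "it will automatically turn itself off after 30 minutes". It also limits the device to two days: "The study device will be used for only 2 days during the post-surgery hospital stay". The usual hospital stay "varies between 48-72 hours post-operatively".

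On pain ratings, the primary-outcome paragraph names medication use over the first 24 and 48 hours as the primary outcome and then adds that "patients will be asked to rate their pain based on a set VAS pain scale twice a day before the IFC treatment". No VAS rating during or after a session is described. The secondary outcomes include pain scores charted by nurses and physical therapists as routine care, with no timing relative to device sessions.

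Section 4, Data analysis, begins its hypothesis with "We hypothesize that IFC therapy will improve patient's pain management" and lists VAS among the study variables. It does not say which VAS ratings are analysed, how they are summarised, or whether the first is a baseline. The named tests are an unadjusted Student's t-test or Mann-Whitney U test.

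**The concern.** A rating taken just before a session shows how the patient feels at the end of the interval since the previous one. It answers whether relief persists, but not whether the session relieved pain at the time. The History section explains the device by gate theory and by blocking of pain signals in the treated area. Under that rationale, relief during and soon after stimulation is a natural thing to look for, and the VAS schedule has no rating there.

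At stake is how a null VAS result would be read. If the arms do not differ, the trial could not tell a device that gives no relief from one whose relief fades before the next session. Ratings that were not taken cannot be recovered later.

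**Working it through.** **Plan's own figure.** The documents give no sample size, SD or effect size for VAS. The only calculation is for 48-hour opioid use (Power/sample size): difference 0.30 × 84.2 = 25.26 mg, SD 44.7, two-sided 0.05, 80% power. The normal formula gives n = 2 × (1.960 + 0.842)² × 44.7² / 25.26² ≈ 49.2, rounded up to 50 per group, as stated. This point does not depend on that figure.

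**Schedule count.** Sessions: 2 per day × 2 days = 4. VAS ratings: 2 per day × 2 days = 4, reading the sentence as one rating before each session.

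| VAS rating | Sessions already received | What it can show |
|---|---|---|
| 1 | 0 | Baseline only |
| 2 | 1 | Relief carried over from session 1 |
| 3 | 2 | Relief carried over from sessions 1–2 |
| 4 | 3 | Relief carried over from sessions 1–3 |
| none | 4 | Session 4 has no study VAS |

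So 1 of 4 ratings is untreated, 3 of 4 measure carry-over, and 0 of 4 sessions have a rating at a fixed time afterwards. The spacing of the two daily sessions is not stated. The carry-over interval is therefore unknown and need not be the same for ratings 2, 3 and 4.

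**Why the role of rating 1 should be written down.** The plan does not say that rating 1 will be averaged with the others, but nothing rules it out. As an illustration, assume a constant effect on ratings 2–4, none on rating 1, equal variances (set to 1) and a common within-patient correlation ρ.

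- The mean of all four ratings carries 3/4 of the effect, with variance (1 + 3ρ)/4.
- The mean of ratings 2–4 carries the full effect, with variance (1 + 2ρ)/3.
- Required sample, mean of four relative to mean of three: [(1 + 3ρ)/4 ÷ 0.75²] ÷ [(1 + 2ρ)/3].
- Adjusting the mean of ratings 2–4 for rating 1 reduces its variance to (1 + 2ρ)/3 − ρ².

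| ρ (assumed) | Sample ratio, four vs three | Variance of mean of 2–4 | Same, adjusted for rating 1 |
|---|---|---|---|
| 0.3 | 0.475/0.5625 ÷ 0.533 = 1.58 | 0.533 | 0.443 |
| 0.5 | 0.625/0.5625 ÷ 0.667 = 1.67 | 0.667 | 0.417 |
| 0.7 | 0.775/0.5625 ÷ 0.800 = 1.72 | 0.800 | 0.310 |
| 0.9 | 0.925/0.5625 ÷ 0.933 = 1.76 | 0.933 | 0.123 |

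Under these assumptions, treating rating 1 as an outcome value would need about 1.6 to 1.8 times the sample. Using it as a covariate gains precision.

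**The case against.** The strongest reply is that a pre-session rating is a legitimate measure of sustained relief. The History section also hopes for less swelling and hematoma, with reduced pain as a secondary result, and relief by that route could last or build up. This stands: the pre-session ratings are worth keeping, and making post-session ratings the only VAS endpoint would change the question.

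A reader might infer that ratings 2–4 fall when the effect is weakest. The documents do not support that. It requires relief to fade between sessions, and no time course for pain relief is given. The Risks section mentions drowsiness, reduced alertness and "gait disturbances for 4-5hours after IFC treatment", but that is one adverse-effect case report, not evidence on how long analgesia lasts. Nor can the loss be sized by assuming a decay curve. With exponential decay, the share of relief left at the next rating is 0.5^(gap/half-life). This runs from 2% (11.5-hour gap, 2-hour half-life) to 74% (3.5-hour gap, 8-hour half-life), and the documents fix neither input.

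It is also fair to say that pain is measured elsewhere. Nursing and physical therapy scores may fall after a session, including the fourth, and therapy may take place with the device running. A KOOS pain score is listed too, without a time point. But none of these is tied to session times, so none can be read as an immediate response or as follow-up of session 4.

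Finally, a pre-treatment rating is an ordinary baseline and not a fault. That is right; the gap is only that Data analysis does not give it that role.

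**Conclusion.** The point holds as a limitation of the VAS measure. On the written schedule, one of four ratings is pre-treatment, three show carry-over only, and session 4 has no study VAS. Short-lived relief would go unseen on VAS. That such relief occurs is plausible from the stated mechanism but is not established by the documents, so no figure is put on the amount missed. The 1.6 to 1.8 sample ratio applies only if rating 1 were pooled with later ratings, which the plan does not state.

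A reader might go further and infer that the whole trial could wrongly conclude that there is no pain benefit. That does not follow. The primary outcome is medication use over 24 and 48 hours, the sample size rests on 48-hour opioid use, and neither depends on when VAS is rated. This is an inexpensive improvement to one pain measure and does not threaten the primary comparison.

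**What to change.** In the primary-outcome paragraph of the Study Design:

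- Keep the rating before each session.
- Add one VAS self-rating at a fixed time after each session, for example when the device switches off at 30 minutes, in both arms and including session 4.
- Record the start time of every session.

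In section 4, Data analysis:

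- Use rating 1 as the baseline covariate, not as an outcome value. For VAS this needs a covariate-adjusted comparison such as ANCOVA, because the tests now listed are unadjusted.
- Report the post-session ratings (immediate relief) and pre-session ratings 2–4 (carry-over) separately, each with a named summary such as the mean.

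The cost is about four extra one-line ratings per patient (from four to eight), two protocol edits and no new instrument. Some post-session ratings may be missed, since the device switches itself off and the patient may be asleep or no staff member may be present. The number missed should be reported by arm.

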# **Study Population**

a. The study population will be adult patients older than 18 with severe knee osteoarthritis that have failed non-operative conservative therapy and now require total knee arthroplasty. All patients will undergo unilateral primary total knee arthroplasty with the Zimmer Persona prosthesis performed by [name].

Pre-operative clearance will be done by the Montefiore Geriatrics team prior to day of surgery. Inclusion criteria: Adult patients with knee osteoarthritis who have failed conservative therapy and undergoing elected TKA.

Exclusion criteria:

i. <18 years old

ii. Any patient with pacemaker or any electrical stimulator device

- iii. Significant baseline deformity (flexion contracture)
- iv. Patient with clinically diagnosed fibromyalgia?
- v. Patients without capacity to consent for the study
- vi. Patients not able to have local nerve block or spinal anesthesia
- vii. Patients with prior opioid use

viii. Patient who is categorized to have `Severe` fear and anxiety responses to pain, according to the PCS survey.

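### Range of motion is part of the stated hypothesis, but the plan names no pre-operative value and no baseline adjustment, so its comparison gives up precision

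*Combined protocol and SAP*

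**What the plan says.** Under Data and Safety Monitoring, item 4 (Data analysis), the hypothesis is that IFC will "improve patient's pain management and range of motion" and reduce edema. Range of motion is also in the list of study variables there.

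The measurement schedule is in the secondary outcomes under Study Design. In hospital: "Range of motion will be recorded during the daily physical therapy sessions", with a goniometer. After discharge, it is "assessed again in clinic at the first post-operative visit". Both are post-operative. The next sentence treats edema differently: "thigh circumference will be calculated at the superior pole of the patella both prior to the surgery and daily post-operatively". The paragraph closes by saying that these outcomes are collected as routine care and held in the patient's chart.

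The Data analysis item compares means by Student's t-test or Mann-Whitney test. It mentions no covariate and no change from baseline, for range of motion or for thigh circumference.

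Power/sample size bases its 50 per group on 48-hour opioid use alone. It plans to start with 25 per group and aims for 20 per group at the end. Nothing there concerns range of motion.

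**The concern.** Patients come to knee replacement with different amounts of knee motion. To the extent that motion before surgery predicts motion after it, those differences are variation that a baseline covariate would remove. The plan leaves them in the error term.

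This matters more in a small trial, and the value cannot be measured once the operation has been done. The plan already uses a pre-operative reading for the other physical outcome in the hypothesis, so the omission looks like an oversight rather than a choice.

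**Working it through.** **The plan's own figure.** From Power/sample size: mean 84.2 mg, SD 44.7, 30% reduction, two-sided 0.05, 80% power.

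- Difference = 0.30 × 84.2 = 25.26 mg.
- n per group = 2 × (1.960 + 0.842)² × (44.7/25.26)² = 49.2, rounded up to 50. The t-based solution is 50.1.

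The stated 50 reproduces. It concerns opioid use only and neither supports nor contradicts this point.

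**Inputs for range of motion.** From the documents: 20 completers per group (25 enrolled), 1:1 allocation, two-sided 0.05. I apply the same 80% power. The documents give no SD for range of motion, so differences are in SD units. They give no pre/post correlation, so r is assumed at 0.3, 0.5 and 0.7.

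**Formulas.**

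- Unadjusted detectable difference = (1.960 + 0.842) × √(2/n). For n = 20 this is 2.802 × 0.316 = 0.89 SD (0.91 SD with the t correction). For n = 25 it is 2.802 × 0.283 = 0.79 SD.
- ANCOVA with one baseline covariate multiplies the variance by (1 − r²), so the detectable difference is multiplied by √(1 − r²).
- The equivalent unadjusted sample size is n/(1 − r²).
- A raw change score multiplies the variance by 2(1 − r), taking the pre- and post-operative SDs as equal.

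| Assumed r | ANCOVA variance factor | Detectable difference, 20 per group | 20 per group acts like | Detectable difference, 25 per group | Change-score variance factor |
|---|---|---|---|---|---|
| no adjustment | 1.00 | 0.89 SD | 20 | 0.79 SD | – |
| 0.3 | 0.91 | 0.85 SD | 22 | 0.76 SD | 1.4 |
| 0.5 | 0.75 | 0.77 SD | 27 | 0.69 SD | 1.0 |
| 0.7 | 0.51 | 0.63 SD | 39 | 0.57 SD | 0.6 |

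A change score is worse than no adjustment when r is below 0.5, and worse than ANCOVA at each r shown.

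**Cost of estimating the slope.** With 40 patients in all, fitting the covariate raises the expected variance by a factor of about 1 + 1/(40 − 4) = 1.03. At r = 0.3 the net factor is 0.91 × 1.03 = 0.94, and the detectable difference is 0.89 × √0.94 = 0.86 SD. The break-even is r² = 1/37, or r of about 0.16.

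**The case against.** Several objections have force.

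- **A value may already exist.** The plan says the outcomes are routine and charted, so pre-operative motion may already be in the record. This stands. The documents support saying that no pre-operative value is named as study data. They do not support saying that none exists.
- **It adds a measurement.** The flexion-contracture exclusion implies some examination of the knee before surgery. It gives no instrument or degree threshold, so it does not show that a goniometer reading is taken. If nothing is charted, one short reading is added, at a pre-operative visit that already takes place.
- **The gain is assumed.** This stands. Motion in the first days may be driven largely by pain and swelling, and excluding contracture may narrow the baseline spread. Both would push r down, and at 0.3 the gain is about 5% in standard error.
- **Recording a baseline alone changes nothing.** This is correct: thigh circumference has one and is still analysed unadjusted. The analysis sentence has to change as well.

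A reader might infer two stronger points. The first is that chance imbalance in pre-operative stiffness could imitate a treatment effect and so bias the result. Allocation is randomised 1:1 in blocks, and an unadjusted test already allows for such imbalance in its 5% error rate. What is lost is precision.

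The second is that range of motion should also be taken at 6 weeks because that visit is otherwise wasted. The Objective is short-term outcome and the device is used for two days, so stopping at the first clinic visit is defensible. Nor is the follow-up period empty: complications and 30-day emergency visits fall within it, and the KOOS pain score has no stated time point.

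**Conclusion.** The point holds as a modest loss of precision on a secondary outcome that is part of the stated hypothesis. At 20 completers per group, ANCOVA would lower the detectable difference from about 0.89 SD to between 0.85 and 0.63 SD for assumed r between 0.3 and 0.7. The true gain may lie near the small end, and it would vanish if r were below about 0.16. These figures assume a linear relation between pre- and post-operative motion with a common slope in both groups.

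The point does not touch the primary outcome or its sample size. It is worth acting on because the cost is small and a baseline that was neither charted nor measured cannot be recovered after surgery.

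**What to change.** - **Secondary outcomes (Study Design):** name a pre-operative goniometer range of motion as study data. Take it from the chart if it is already recorded there, otherwise by one reading at the pre-operative visit.
- **Data analysis:** analyse post-operative range of motion by ANCOVA with the pre-operative value as covariate, and not as a raw change score. Analyse post-operative thigh circumference in the same way, using the pre-operative value already planned.

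The cost is one or two sentences in the plan and, if the value is not already charted, one short non-invasive reading per patient. No extra visit or enrolment is needed.
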